7.10.1.2 Imputation of Adverse Event Onset Date

For AEs, a missing or incomplete onset date will be imputed according to the following conventions:

If an onset date is missing or only the year is known, the imputed onset date will be the latest of the following non-missing dates:

1. Date of first dose of double-blind treatment
2. Date of randomization visit + 1 day
3. Date of last dose of single-blind run-in study drug + 1 day

If only the month and year is known for onset date, set the surrogate onset date to the first day of that month and then apply the following rules:

- If the month and year of the onset date is prior to the month and year of the first dose of double-blind treatment, then the surrogate onset date will be the imputed onset date.
- If the month and year of the onset date is on or after the month and year of the first dose of double-blind treatment or if the first dose of double-blind treatment is missing, then the imputed onset date will be the latest of the following non-missing dates:

4. Date of first dose of double-blind treatment
5. Date of randomization visit + 1 day
6. Date of last dose of single-blind run-in study drug + 1 day
7. Surrogate onset date

If the imputed onset date is after a complete adverse event end date, the imputed onset date will be the same as the complete adverse event end date.

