6.2 Safety Variables

Safety will be assessed by evaluation of the following variables:

- Treatment-emergent adverse events (TEAEs; frequency, severity, seriousness, and relationship to study drug).
- Adverse Events of Possible Hepatic Origin (See [Appendix 1](#))
- Acute Urinary Retention
- Urinary Tract Infections
- Clinical laboratory variables (hematology, biochemistry including liver function tests, and urinalysis)
- Cardiovascular events, vital signs (systolic and diastolic blood pressure and pulse rate), MI, Stroke and serious arrhythmias.
- Montreal Cognitive Assessment (See [Appendix 5](#))
- Physical Examination
- 12-lead electrocardiogram (ECG)
- Post-Void Residual Volume

TEAE is defined as an adverse event observed after starting administration of the test drug/comparative drug. If the adverse event occurs on Day 1 and the onset check box is marked “Onset after first dose of study drug” or the onset check box is left blank, then the adverse event will be considered treatment emergent. If the adverse event occurs on Day 1 and the onset check box is marked “Onset before first dose of study drug”, then the adverse event will not be considered treatment emergent. If a subject experiences an event both during the pre-investigational period and during the investigational period, the event will be considered as a TEAE only if it has worsened in severity (i.e. it is reported with a new start date). All adverse events collected that begin within 30 days after taking the last dose of study drug will also be counted as TEAEs.

A drug-related TEAE is defined as any TEAE with possible or probable relationship to study treatment as assessed by the investigator or with missing assessment of the causal relationship.

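### A recorded onset year is ignored when only the year of an adverse event is known, so a few events can be dated, and some counted as TEAEs, against the recorded year

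*SAP*

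**What the plan says.** SAP 7.10.1.2 gives one rule for two situations: "If an onset date is missing or only the year is known, the imputed onset date will be the latest of the following" non-missing dates. The candidates are:

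- "Date of first dose of double-blind treatment"
- "Date of randomization visit + 1 day"
- "Date of last dose of single-blind run-in study drug + 1 day"

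None of the three depends on the recorded year.

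The next rule in the section, for a known month and year, does use what was recorded. It builds a surrogate date on the first of that month. "If the month and year of the onset date is prior to the month and year of the first dose of double-blind treatment", the surrogate stands and the event stays pre-treatment. Otherwise the surrogate joins the list from which the latest date is taken.

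A closing sentence limits every imputed onset: "If the imputed onset date is after a complete adverse event end date, the imputed onset date will be the same as the" end date.

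The imputed date feeds the classification in SAP 6.2: "TEAE is defined as an adverse event observed after starting administration of the test drug/comparative drug", with a tail of 30 days after the last dose. For a Day 1 event, a check box marked as onset before the first dose makes it non-emergent; a blank box makes it a TEAE. SAP 7.5.1 also plans TEAE tables before and after titration. Under SAP 7.10.1, AE listings show the actual partial date and not the imputed one.

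**The concern.** Assigning an event to treatment is a reasonable way to resolve doubt about timing. With a year-only onset there is sometimes no doubt. If the recorded year precedes the year of first dose, every possible day and month puts the onset before treatment, yet the rule can make the event a TEAE. If the recorded year follows the first-dose year, every possible completion falls on or after 1 January of the later year, yet the rule dates the event in the year before.

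Three nearby rules keep a known year: the month-and-year rule in the same section, the concomitant medication rule in SAP 7.10.1.3 (a missing month becomes January), and the OAB onset rule in SAP 7.10.1.4 (30 June of the recorded year). The year-only AE rule is out of line with all three.

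At stake are the TEAE count for earlier-year events and, for later-year events, their place in the titration tables. A listing could also show a bare 2015 for an event counted as a TEAE in a subject first dosed in 2016, with nothing to explain it.

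**Working it through.** The plan states no figure for this rule, so there is none to reproduce. The check applies the rule as written to example dates and then estimates how often it can bite.

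**Step 1. The rule applied literally.** Onset = latest of (first dose, randomization visit + 1 day, last run-in dose + 1 day), set back to a complete end date if that is earlier. An event is a TEAE if onset lies between first dose and last dose + 30 days. The dates are illustrative. The randomization visit and last run-in dose are the day before first dose, except in row 4.

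| Recorded year | First dose | End date | Imputed onset | TEAE? |
|---|---|---|---|---|
| 2015 | 12 Jan 2016 | none or incomplete | 12 Jan 2016 (Day 1) | yes, unless box marked before dose |
| 2015 | 12 Jan 2016 | 5 Jan 2016 | 5 Jan 2016 | no (end-date cap) |
| 2015 | 12 Jan 2016 | 5 Feb 2016 | 12 Jan 2016 (Day 1) | yes, unless box marked before dose |
| 2015 | 11 Jan 2016, same day as randomization; last run-in dose 10 Jan | none | 12 Jan 2016 (Day 2) | yes; check box does not apply |
| 2016 | 10 Nov 2015 | none, or 20 Jan 2016 | 10 Nov 2015 (Day 1) | yes, but wrong year |
| 2015 | 10 May 2015 | none | 10 May 2015 (Day 1) | yes; no conflict with the year |

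In row 5 the imputed date is Day 1, so in a subject titrated at Week 4 or Week 8 the event always counts as before titration.

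**Step 2. Can it happen?** AE collection starts at informed consent (protocol 5.4.4). Baseline is 18 to 38 days after Screening (protocol Table 1, footnote a). Double-blind treatment lasts 12 weeks = 84 days, and the TEAE tail adds 30, giving 114. The planned study period, 3Q2014 to 4Q2016 (protocol synopsis), crosses two year-ends. So it can.

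**Step 3. How often?** An event has the wrong year only if New Year falls between it and the first dose. Assume first doses are spread evenly over the year and events evenly over their window of W days. The mean distance from first dose is then W/2, and the chance that New Year lies in between is (W/2)/365.

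- Pre-treatment, W = 38 (the maximum): 19/365 = 5%
- On treatment or in the tail, W = 114: 57/365 = 16%

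**Step 4. Number of events.** The documents give no count of year-only onsets. Assume 4 to 10.

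- Mis-dated: from 4 × 5% = 0.2 (all pre-treatment) to 10 × 16% = 1.6 (all on treatment or in the tail), so about 0 to 2.
- Changing TEAE status: only earlier-year events can. Even if all were pre-treatment and none were caught by the cap or the check box, 4 × 5% = 0.2 to 10 × 5% = 0.5, so typically 0 to 1.

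**The case against.** The strongest reply is that this is a conservative safety convention, applied alike in both arms, with safeguards around it. Much of that stands.

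- A reader might infer that every event known to be pre-treatment becomes a TEAE. The text does not support this. The end-date cap protects any event with a complete end date before first dose, and the Day 1 check box can protect others. Still exposed are events that are ongoing, have an incomplete end date, or ended after first dose. For these the check box helps only if it is marked and the imputed date is Day 1.
- A reader might infer that the two rules contradict each other. They do not: no onset falls under both. They are inconsistent in how much recorded information they use.
- A reader might size the problem by the share of subjects whose window crosses a New Year: 38/365 = 10% before treatment and 114/365 = 31% on treatment or in the tail. Applied to 10 events, the latter gives about 3. That overstates it, because an event in such a subject is wrong only if it lies on the far side of New Year from the first dose.
- Later-year events normally remain TEAEs under either date, and the listings keep the recorded year visible. What is left for them is the titration tables, and only for events that truly followed titration.
- Sites must keep eCRF entries complete and answer queries (protocol 8.1.1), so year-only onsets may be close to none.

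What does not stand is the appeal to conservatism for an earlier-year event. Conservatism settles uncertainty, and here the recorded year leaves none.

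**Conclusion.** The point holds in a limited form. For a year-only onset, SAP 7.10.1.2 discards the recorded year and can produce a date, and sometimes a TEAE classification, that no completion of the recorded date could give.

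The size is small: about 0 to 2 mis-dated events, with typically 0 to 1 changing TEAE status. That rests on evenly spread first doses and events, the longest permitted windows, and an assumed 4 to 10 year-only onsets. No efficacy result depends on it. It is a minor correction, worth making because the rule is plainly wrong in the cases it affects and is cheap to repair.

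**What to change.** Separate the year-only case from the wholly missing case in SAP 7.10.1.2:

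- **Recorded year earlier than the first-dose year:** impute 31 December of that year; the event is not a TEAE.
- **Same year, or first-dose date missing:** keep the present rule.
- **Recorded year later than the first-dose year:** impute the latest of the present dates and 1 January of the recorded year.

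Keep the end-date cap for all three, and keep the present rule for wholly missing dates.

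The fix removes dates known to be wrong, but does not settle every titration assignment. With first dose on 10 November, a Week 8 titration falls 56 days later, about 5 January, so an onset imputed to 1 January still counts as before titration.

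The cost is about two lines of SAP text and the matching code. SAP section 1 allows revisions before database hard lock.

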7.10.1.3 Imputation of Concomitant Medication and Non-Drug Treatment Start and End Date

Start and stop dates for all concomitant medications and non-drug treatment are collected on the eCRF. However, in case of missing or partial information in these dates, the following rules will be used:

If start date is missing or partial:

8. if month is missing, use January
9. if day is missing, use the first day of the month under consideration
10. if year is missing, use year of the informed consent date
11. if entire date is missing, use informed consent date

If stop date is missing or partial and the medication is not ongoing:

12. if month is missing, use December
13. if day is missing, use the last day of the month under consideration
14. if year or the entire date is missing, set to December 31st, 2099

If the imputed start date is after the stop date, then the imputed start date will be one day prior to the stop date.

If the medication or non-drug treatment is ongoing, the stop date will remain missing.

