12 APPENDICES

12.1 Appendix 1: List of Prohibited and Restricted Concomitant Medications

Part A – Prohibited Medications

Use of these medications in any formulation is not permitted between Screening (Visit 1) and Week 12/End of Treatment (Visit 6). This list is not exhaustive. In case of doubt, the Investigator must contact the local study monitor. These medications must have been discontinued at least 30 days prior to Screening (Visit 1). Current or previous use of mirabegron at any time is prohibited.

Anticholinergics/Antispasmodics		
Atropine	Baclofen	Biperiden
Bentropine/Benzatropine	Clomipramine	Cyclobenzaprine
Darifenacin	Dicyclomine/Dicycloverine	Emepronium
Glycopyrronium/Glycopyrrolate	Fesoterodine	Flavoxate
Glycopyrrolate	Hyoscine	Hyoscyamine
Ipratropium	Isopropamide	Meclozine
Orphenadrine	Otilonium	Oxybutynin
Oxyphencyclimine	Procyclidine	Propantheline
Propiverine	Scopolamine/(Butyl)hyoscine	Solifenacin
Tiotropium	Tolterodine	Trospium
CYP2D6 Substrates with Narrow Therapeutic Index		
Aripiprazole (neuroleptic)	Desipramine (TCA)	Donepezil (Acetylcholinesterase inhibitor)
Thioridazine (anti-psychotic)	Flecainide (anti-arrhythmic)	Propafenone (anti-arrhythmic)
Imipramine (TCA)	Tramadol (analgesic)	Venlafaxin (SNRI)
OAB Medications		
Mirabegron	Other medication if used to treat OAB	
Medications to Treat Dementia		
Donepezil	Rivastigmine	Galantamine
Memantine	Other medication if used to treat dementia	

Part B - Medications Permitted With Restrictions

Medications restricted between Screening (Visit 1) and Week 12/End of Treatment (Visit 6) include loop diuretics, alpha blockers and 5-Alpha reductase inhibitors. All medications in Part B of Appendix 1 are permitted provided the subject has been taking this medication on a long-term basis, i.e., has not stopped, or started or changed dose within the 30 days prior to Screening (Visit 1), no new drug of the same class has been added to the regimen within the 30 days prior to Screening (Visit 1), and the subject remains on the medication at the same dose during the course of the study.

Loop Diuretics		
Furosemide	Bumetanide	Piretanide
Alpha Blockers		
Alfuzosin	Doxazosin	Prazosin
Phenoxybenzamine	Phentolamine	Tamsulosin
Terazosin		
5-alpha Reductase Inhibitors		
Dutasteride	Finasteride	

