5.2.1 Reasons for Exclusion From PPS

The following criteria listed in Table 3 may lead to subject's exclusion from PPS.

Table 3. Criteria for Assessing Major Protocol Violations which could potentially Impact Efficacy Assessments

Number	MPV Criteria
Treatment Violations	
1	Double Blind treatment duration of less than 53 days
2	No measurement of the primary efficacy endpoint available at or after Visit 2
3	Treatment compliance of less than 70% between randomization and last visit
4	Administration of excluded concomitant treatment as described in the Study Protocol.
Inclusion Criteria Violations	

5	Subject did not experience at least one incontinence episode based on the 3-day micturition diary at baseline.
6	Subject did not experience at least 3 episodes of urgency (grade 3 or 4) based on the 3-day micturition diary at baseline.
7	Subject did not experience an average of greater than or equal to 8 micturitions/day based on the 3-day micturition diary at baseline.
Exclusion Criteria Violations	
8	Subject was non-compliant during 2-week placebo run-in period, defined as taking less than 80% or greater than 120% of study medication
9	Subject did not complete all 3 days of the baseline 3-day micturition diary
10	Unblinding of Study Drug
11	Error in Study Drug Administration
Other Exclusions from PPS	
12	Subject did not complete at least 2 days of the EOT 3-day micturition diary

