6.3.3 Previous, Prohibited, and Concomitant Medication

Previous Medication

Previous medication is defined as medication with at least one dose taken before the date of the first dose of study drug in the run-in period (i.e. first or last medication intake is prior to first placebo run-in dose date (exclusive)). All previous OAB medications, regardless of when they were taken, will be collected on the eCRF. Previous non-OAB medications will only be collected on the eCRF if taken within 30 days prior to screening.

Prohibited Medication

Use of these medications in any formulation is not permitted between Screening (Visit 1) and Week 12/End of Treatment (Visit 6). This list is not exhaustive. In case of doubt, the Investigator must contact the local study monitor. These medications must have been

discontinued at least 30 days prior to Screening (Visit 1).

Table 5. Part A –Prohibited Medications

Anticholinergics/Antispasmodics		
Atropine	Baclofen	Biperiden
Bentropine/Benzatropine	Clomipramine	Cyclobenzaprine
Darifenacin	Dicyclomine/Dicycloverine	Emepronium
Glycopyrronium/Glycopyrrolate	Fesoterodine	Flavoxate
Glycopyrolate	Hyoscine	Hyoscyamine
Ipratropium	Isopropamide	Meclozine
Orphenadrine	Otilonium	Oxybutynin
Oxyphenacyclimine	Procyclidine	Propantheline
Propiverine	Scopolamine/(Butyl)hyoscine	Solifenacina
Tiotropium	Tolterodine	Trospium
CYP2D6 Substrates with Narrow Therapeutic Index		
Aripiprazole (neuroleptic)	Desipramine (TCA)	Donepezil (Acetylcholinesterase inhibitor)
Thioridazine (anti-psychotic)	Flecainide (anti-arrhythmic)	Propafenone (anti-arrhythmic)
Imipramine (TCA)	Tramadol (analgesic)	Venlafaxin (SNRI)
OAB Medications		
Mirabegron	Other medication if used to treat OAB	
Medications to Treat Dementia		
Donepezil	Rivastigmine	Galantamine
Memantine	Other medication if used to treat dementia	

Part B -Medications Permitted With Restrictions

Medications restricted between Screening (Visit 1) and Week 12/End of Treatment (Visit 6) include loop diuretics, alpha blockers and 5-Alpha reductase inhibitors. All medications in Part B of Appendix 1 are permitted provided the subject has been taking this medication on a long-term basis, i.e. has not stopped, or started or changed dose within the 30 days prior to Screening (Visit 1), no new drug of the same class has been added to the regimen within the 30 days prior to Screening (Visit 1), and the subject remains on the medication at the same dose during the course of the study.

Concomitant Medication

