Concomitant medication during the placebo run-in period is defined as medication with at least one dose taken between the date of first dose (inclusive) of run-in study medication and the date of first dose (not inclusive) of double-blind study drug

Concomitant medication during the double-blind treatment period is defined as medication with at least one dose taken between the date of first dose (inclusive) of double-blind study medication and the last dose of double-blind treatment (inclusive)

For above variables, imputation methods will be used in case of missing medication intake dates.

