7.10 Handling of Missing Data, Outliers, Visit Windows, and Other Information

7.10.1 Missing Data

Missing primary and secondary efficacy endpoints will be handled by LOCF for continuous variables, and non-responder imputation for binary variables.

For all OAB-q scales and subscales, if <50% of the items are missing, the scale/subscale should be retained with the mean scale score of the items present used to impute a score for the missing items. If >=50% of the items are missing, no scale/subscale score should be calculated, the scale/subscale score should be considered missing.

As a general principle, imputation of missing dates for variables will not be done. Exceptions are for start and stop dates of study drug intake, AEs and concomitant medications. The imputed dates will be used to determine whether the medication was taken prior to or during the double-blind treatment period. Listings of the AEs and concomitant medications will present the actual partial dates; imputed dates will not be shown.

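### SAP 7.10.1.3 dates a stopped medication with no stop year to 31 December 2099, so an OAB drug already recorded as stopped at Visit 1 would usually be tabulated as taken during double-blind treatment

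*SAP*

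**What the plan says.** Four parts of the SAP act together.

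- **The rule (SAP 7.10.1.3).** It applies as follows: "If stop date is missing or partial and the medication is not ongoing". A missing month becomes December and a missing day the last day of the month. For anything worse: "if year or the entire date is missing, set to December 31st, 2099". On the start side: "if entire date is missing, use informed consent date". The only ordering check moves an imputed start back to the day before the stop. Nothing limits how late the imputed stop may be.
- **What the dates are for (SAP 7.10.1).** "The imputed dates will be used to determine whether the medication was taken prior to or during the double-blind treatment period". The same section says that listings show the actual partial dates and not the imputed ones.
- **What is collected (SAP 6.3.3).** "All previous OAB medications, regardless of when they were taken, will be collected on the eCRF". Other drugs are collected only for the 30 days before screening.
- **How a drug becomes concomitant (SAP 6.3.3).** "Concomitant medication during the double-blind treatment period is defined as medication with at least one dose taken between the date of first dose" and the last double-blind dose, both inclusive. The section adds that imputation is used for these variables when intake dates are missing.

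SAP 7.2.4 tabulates previous and concomitant medication by treatment group in the SAF. OAB drugs are on the prohibited list (Protocol Appendix 1 Part A; SAP Table 5). Criterion 4 in SAP Table 3 (section 5.2.1) is "Administration of excluded concomitant treatment as described in the Study Protocol", and deviation PD4 covers the same event.

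**The concern.** Assuming late use is a reasonable convention when nothing is known about when a drug ended. Here something is known. Both schedules of assessments take the medication and OAB-medication history at Visits 1 and 3. A drug entered at Visit 1 as no longer taken had ended by that visit, yet the rule extends it through the whole treatment period.

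Unknown stop years are most likely where recall is open-ended, and only OAB drugs are collected without a time limit. The misclassified records would thus tend to be prohibited drugs, and the subjects concerned those with earlier OAB treatment. A reader of the safety-set tables would see antimuscarinics and other OAB drugs apparently taken during treatment. The matching listing would show a blank stop date, with nothing to explain the difference.

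The SAP bounds other imputed dates by known facts. An imputed AE onset may not fall after a complete AE end date (7.10.1.2), and an imputed OAB symptom onset may not fall after consent (7.10.1.4). The medication stop date has no such bound.

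**Working it through.** The plan states no figure to reproduce. The check applies the rules of SAP 7.10.1.3 and the definitions of SAP 6.3.3 literally to example records.

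**Calendar (illustrative assumption):** consent 1 June 2015; first run-in dose 15 June 2015; double-blind treatment 29 June to 20 September 2015.

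**Flags:**
- previous: start before the first run-in dose
- run-in concomitant: start before the first double-blind dose and stop on or after the first run-in dose
- double-blind concomitant: start on or before the last double-blind dose and stop on or after the first

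All records are marked not ongoing.

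| Start recorded | Stop recorded | Imputed interval | Previous | Run-in | Double-blind |
|---|---|---|---|---|---|
| 1 Mar 2008 | all missing | 1 Mar 2008 to 31 Dec 2099 | yes | yes | **yes** |
| 1 Mar 2008 | 10 May, year missing | 1 Mar 2008 to 31 Dec 2099 | yes | yes | **yes** |
| 2008 only | all missing | 1 Jan 2008 to 31 Dec 2099 | yes | yes | **yes** |
| all missing | all missing | 1 Jun 2015 to 31 Dec 2099 | yes | yes | **yes** |
| 1 Mar 2008 | 2015 only (consent year) | 1 Mar 2008 to 31 Dec 2015 | yes | yes | **yes** |
| 1 Mar 2008 | 2010 only | 1 Mar 2008 to 31 Dec 2010 | yes | no | no |
| all missing | 1 May 2010 | 30 Apr 2010 to 1 May 2010 | yes | no | no |
| November, year missing | all missing | 1 Nov 2015 to 31 Dec 2099 | no | no | no |

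The first five rows are misclassified if the drug had in fact ended before Visit 1. The next two are right. In the last row the imputed start falls after the last dose, so the record escapes the double-blind flag but also drops out of previous medication. This exception is why the conclusion says usually and not always.

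**Year-only stop in the consent year.** The imputed 31 December falls on or after the first double-blind dose unless consent came late in the year. Protocol Table 1, footnote a, puts Baseline 18 to 38 days after Visit 1. Assume consent at Visit 1, consent dates uniform over the year and the first dose on the Baseline day:

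- 18 days: (365 − 18)/365 = 95%
- 28 days: (365 − 28)/365 = 92%
- 38 days: (365 − 38)/365 = 90%

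These are shares of consent dates, given that such a record exists. They do not say how often one occurs.

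**Number of subjects.** This would need the proportion with past OAB drugs and the proportion of those with an unknown stop year. The documents give neither. For scale only, each 1% of the 800 planned subjects is 8 subjects.

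**Would a Visit 1 cap work?** Baseline is at least 18 days after Visit 1 and at most 17 days after Visit 2, so Visit 2 is at least 18 − 17 = 1 day after Visit 1. A stop date no later than Visit 1 therefore precedes the first run-in dose, and the record counts as previous only. With the cap, the last row of the table would start on 31 May 2015 under the existing ordering check and would also be previous.

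**The case against.** The strongest objections concern consequence and scope.

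- **No efficacy inference depends on this.** Correct. FAS-I membership (SAP 5.1) uses dosing and diary data, not medication. What is established is an error in descriptive tables.
- **PPS exclusion does not follow.** A reader might infer that these records automatically meet criterion 4, so that adherent subjects leave the PPS. The documents do not support that. Neither criterion 4 nor PD4 is said to use imputed dates. Protocol 8.1.6 has deviations identified and notified to the sponsor. Table 3 criteria only may lead to exclusion, detailed set criteria sit in separate Classification Specifications, and the ASCM decides before unblinding (SAP 5.2). The listings show true partial dates. What remains is a possible false query, if the flags are programmed from imputed dates.
- **The rule's heading names concomitant medication and non-drug treatment, not medication history.** This does not remove the problem, because 6.3.3 and 7.10.1 extend imputation to the prior-versus-during decision. Whether the eCRF lets an OAB-history record lack a stop year, or marks it as ended before the study, cannot be seen from the documents.
- **Sites must establish that prohibited drugs ended at least 30 days before Screening.** This should make a recent stop with an unknown month uncommon. It does less for drugs stopped years ago.
- **A late imputed date is conservative.** That holds for records first entered after randomization. It does not justify overriding a Visit 1 record that the drug had ended.

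**Conclusion.** The point stands as a defect in a stated rule. A not-ongoing OAB drug with a missing stop year, recorded at Visit 1 as already stopped, would usually be tabulated as taken during double-blind treatment. A stop known only as the consent year can be misclassified in the same way.

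The title of the rule might suggest that all past OAB drugs are affected. They are not: a known earlier stop year gives the right answer. Nor does the SAP derive a prohibited-medication flag from dates; that label follows only because OAB drugs are on the Part A list.

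The certain effect is on the SAF concomitant-medication tables. An effect on PPS criterion 4 or PD4 is conditional on programming that the SAP does not describe. The FAS-I results do not change. The conclusion assumes that the eCRF permits a missing stop year and that the rule is programmed as written. The change is worth making because it is cheap and the present rule can contradict recorded information.

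**What to change.** Add to SAP 7.10.1.3:

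1. For a medication recorded as stopped in the Visit 1 medication or OAB-medication history, the imputed stop date may not be later than the Visit 1 date. It then counts as previous only.
2. For a medication first recorded as stopped between Visit 1 and Visit 3, the imputed stop date may not be later than the day before the first double-blind dose. It stays eligible to count as run-in concomitant and for prohibited-medication review, so genuine use between those visits is not hidden.
3. Imputed dates alone do not trigger PPS criterion 4 or PD4. This is needed even with the cap, because a stop date set at Visit 1 would on its face breach the 30-day requirement.
4. The 31 December 2099 rule stays for records first entered after randomization.

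The cost is a few lines of SAP text and a programming condition. No endpoint, eligibility rule or primary analysis changes. The small downside is that a drug wrongly recorded as stopped would not be flagged by date alone.
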